7.0 ADVERSE EVENT REPORTING

7.1 CLASSIFICATION OF ADVERSE EVENTS

The ACCESS study uses the definitions of an adverse event (AE) and a serious adverse event (SAE) established by the International Conference on Harmonization (ICH) guidelines on Clinical Safety Data Management (32). These definitions are:

An adverse event (also known as “non-serious adverse event” (**NSAE**)) is any untoward medical occurrence in a patient or clinical investigation subject administered a study intervention and which does not necessarily have a causal relationship with this treatment. An adverse event can therefore be any unfavorable and unintended sign (including an abnormal laboratory finding), symptom, or disease temporally associated with the use of an intervention, whether or not considered related to the intervention. Note that adverse changes in the outcome measures of the study (e.g., pain scores) are not considered adverse events and will not be reported as such. Symptoms or other abnormalities that were present prior to a participant's randomization will not be considered adverse events (i.e., these will be treated as pre-existing conditions and not-study related); similarly, therapies (e.g., surgery) to treat a pre-existing condition are not reportable adverse events. Note that clinically meaningful *worsening* of a pre-existing condition is considered an adverse event and will be reported as such.

A Serious Adverse Event (SAE) is any untoward medical occurrence that:

- 1) results in death
- 2) is life-threatening

- 3) requires inpatient hospitalization or prolongation of existing hospitalization
- 4) results in persistent or significant disability/incapacity
- 5) is a congenital abnormality or birth defect
- 6) is an important medical event that may not result in death, be life-threatening or require inpatient hospitalization but if, based on appropriate medical judgment, it may jeopardize the patient and may require medical or surgical intervention to prevent a serious adverse event.

An Unanticipated Problem (UP) is a subset of adverse events with special reporting requirements. The definition of a UP is:

- 1) It is unanticipated (in nature, severity, and/or frequency), and
- 2) It is at least possibly related to participation in research, and
- 3) It suggests greater risk of harm to participant(s) or others than previously known or recognized (includes participants, family members, and research staff).

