1.2 BACKGROUND

TKA is a successful treatment option for end-stage arthritis of the knee. With an aging population and expanding indicated age-range, the annual volume of TKA surgery in the United States currently exceeds 600,000 cases and is projected to continue to increase over the next decade (1,2). Within Kaiser Permanente, we perform over 7,000 TKAs annually in Northern California alone. Published success rates following TKA surgery vary depending on the definition of success but patient satisfaction rates of at least 80% are typical (3). While causes of dissatisfaction following TKA surgery are varied, pain is the most common reported reason (4). Further, published data reported from our own institution has found that the most frequent cause of early inpatient readmission and ED visits after TKA surgery is pain (5). Pain is also one of the primary reasons patients are unable to be discharged home directly after surgery in our institution.

The last decade has seen several significant advances in the management of pain following TKA surgery. “Multi-modal anesthesia” protocols have been developed to utilize non-opioid therapies during the recovery period (6). Historically TKA patients were prescribed Patient-Controlled Analgesia machines to self-administer parenteral opioid-based pain medication. While their use enabled patients to take control of their pain medication administration, the negative impact of these parenteral opioids – including dizziness, nausea, vomiting and respiratory depression – on their recovery after surgery has been well-described (7,8).

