Inpatient hospital admission is one of the greatest contributors to the cost of the episode of care. In the last 7 years we have seen our length of stay for total knee replacement patients reduced from 3 days to less than one day. One of the major hurdles in safe patient discharge after TKA surgery is adequate pain control. The adoption of a multi-modal pain reduction strategy and, in particular, the use of the peri-articular injection has facilitated this reduction in LOS. Part of the rationale for the addition of adductor canal catheters to this pain-reduction strategy is to help improve post-operative pain and reduce LOS. In KPNC SLN, where we perform over 1,000 primary unilateral TKA surgeries each year, utilization of ACCs is variable among surgeons. Comparing length of stay in our primary TKA patients, we see the same rate of same day discharge among providers who use ACCs and those who do not. Further, a pilot study conducted at our facility in 2018 found only a very small (and clinically unimportant) difference in post-operative day 2 (when the effects of the PAI would be expected to have worn off) numerical pain score between patients with an ACC and those without. These findings are similar to a recently published randomized control study which found no difference in pain levels or opioid consumption between TKA patients with PAI alone or with PAI plus ACB (18). Our pilot study has also identified several complications associated with ACCs including leaking, dislodging, bleeding, hematoma development and prolonged neuropraxia, resulting in ED visits and phone calls to address these issues.

The entire cost of adductor canal catheters includes the pump, tubing and medication as well as the FTE provider who places them and the potential cost of ED visits or phone calls/office visits to address complications associated with the catheters. Given the cost of the catheters themselves (\$400) and the number of primary TKA surgeries performed annually in KPNC alone (> 7,000), the annual cost to our organization is estimated to be more than \$4 million.

Therefore, we propose this randomized, open-label, parallel-comparison noninferiority clinical trial to determine whether the effectiveness of these catheters justifies their cost.

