2.2 SECONDARY OBJECTIVES

Among a sample of patients undergoing elective primary unilateral TKA who receive peri-articular anesthetic injections:

- 1) To compare the overall two-week levels of postoperative pain between those participants randomized to ACCs containing ropivacaine and those participants randomized to usual care without an ACC
- 2) To compare the use of opioid medications (in mean total morphine milligram equivalents) between those participants randomized to ACCs containing ropivacaine and those participants randomized to usual care without an ACC over the two-week postoperative period
- 3) To estimate the incidence of complications related to ACC placement including infection, displacement, ACC-related outpatient clinic or ED visits
- 4) To conduct exploratory analyses to identify candidate predictors of differential response to the ACC; potential interacting variables for these analyses will include demographics, baseline pain NRS scores, clinical comorbidities and secondary outcome measures.

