4.0 MEASUREMENTS

4.1 PRIMARY OUTCOME

The primary outcome measurement for this study is the Numerical Rating Scale for pain recorded on the second postoperative day. The pain NRS is a 0-to-10 ordinal scale (with anchors, 0 = "no pain" and 10 = "worst possible pain") which the participant selects in response to the prompt, "What number best describes your typical pain in the past 24 hours?". Several different variations of pain-intensity measures exist but there is good evidence that numerical rating scales are easy to administer

with high respondent acceptability, high reliability (21,22), excellent validity when compared to visual analogue scales (21) and widely recommended as a core measure in pain trials (23).

The primary outcome will be obtained by the study Research Assistant via a telephone call on the second postoperative day. If the Research Assistant is unable to reach the participant by phone, the pain NRS score for the second postoperative day on the daily diary will be used for this measurement, if the diary is returned to the DOR.

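### The adverse-event note in section 7.1 is not limited to recorded pain scores, so ED visits for pain can go unrecorded and are not compared by arm, while catheter-related ED visits are counted

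*Combined protocol and SAP*

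**What the plan says.** Section 7.1 defines the two event classes separately. The first paragraph begins "An adverse event (also known as “non-serious adverse event", so the protocol uses AE for the non-serious class. That paragraph holds this sentence: "adverse changes in the outcome measures of the study (e.g., pain scores) are not considered adverse events and will not be reported as such". A few lines later it says that worsening, if clinically meaningful, "of a pre-existing condition is considered an adverse event and will be reported as such". The SAE definition follows as its own list, and its third criterion is an untoward occurrence that "requires inpatient hospitalization or prolongation of existing hospitalization". The list makes no exception for pain, and the section does not say which rule prevails when two of them apply.

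Pain is the trial's main outcome. Section 4.1 reads "The primary outcome measurement for this study is the Numerical Rating Scale for pain recorded on the second postoperative day", and section 4.2 adds the number of oxycodone tablets taken.

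Section 1.2 reports from the institution's own published data that "the most frequent cause of early inpatient readmission and ED visits after TKA surgery is pain", and adds that pain often keeps patients from going straight home. In setting out what catheters cost, the same section includes "the potential cost of ED visits or phone calls/office visits to address complications associated with the catheters".

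On safety outcomes, Secondary Objective 3 in section 2.2 covers "complications related to ACC placement including infection, displacement, ACC-related outpatient clinic or ED visits". Section 1.3 restricts the safety outcome to events attributed to the ACC, and Secondary Aim 3 in section 8.2 summarizes ACC complications only. Section 1.3 also plans an EMR search for adverse events that concentrates on ED and inpatient encounters.

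**The concern.** The trial tests whether an analgesic device can be omitted. The visits that omission might plausibly cause are return visits for pain. The note in 7.1 sets pain aside as an outcome without saying whether it means the number on the scale or also the clinical event that severe pain leads to.

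The stake is balance. The protocol's case on cost counts ED visits that catheters cause, and Objective 3 gives those visits a place in the results. ED visits for uncontrolled pain have no such place and may not even be recorded as AEs. A reader weighing the catheter's burden against its benefit would then see one side of the acute-visit ledger.

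The trial is open-label, so loose wording can also be applied differently by arm. As an illustration, a participant who comes to the ED in pain after a catheter has dislodged would count under Objective 3. A participant without a catheter who comes with the same pain could be classed as showing a change in outcome.

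**Working it through.** The point rests on no stated figure, so the check sets the passages side by side for each kind of event.

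| Event caused by pain | Note in 7.1 | SAE criterion 3 | Objective 3 / Secondary Aim 3 | Compared by arm in 8.2 |
|---|---|---|---|---|
| Higher recorded NRS score | Excluded, clearly | Not met | Not counted | Yes (primary analysis, Secondary Aim 1) |
| ED visit, no admission | Can be read as excluded | Not met | Not counted unless ACC-related | No |
| Readmission | Can be read as excluded | Met on a plain reading | Not counted unless ACC-related | No |
| Prolonged stay | Can be read as excluded | Met on a plain reading | Not counted unless ACC-related | No |

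**Recorded score.** The exclusion is sound. The values are analysed by arm, and reporting them again as AEs would add nothing.

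**ED visit without admission.** This is the clear gap. Criterion 3 needs hospitalization. Criterion 6, the important medical event, could apply only by case-by-case judgment. The rule on worsening of a pre-existing condition points towards reporting, since knee pain usually predates surgery, but it conflicts with the note and no precedence is given. The visit is not a catheter complication, so Objective 3 does not pick it up.

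**Readmission or prolonged stay.** Criterion 3 is met, and the note stands in the paragraph for non-serious events. On that reading the event is an SAE. The reading is not stated, however, and nothing stops staff from applying the note to both classes.

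**Whether later steps close the gap.** Three routes bring events to notice: the telephone enquiries in 6.6 and 6.7, the EMR search in 1.3, and the reports to the DSM and IRB in 7.2 and 7.3. The enquiries ask about adverse events, the EMR search is for adverse events, and the reports list events already classed as AE or SAE. Each therefore depends on the definition in 7.1. An ED visit for pain may be found in the EMR and still be set aside at classification. The 24-week extraction in 6.8 is aimed mainly at SAEs from week two onwards, so it does not help with an early ED visit that is not serious.

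**The case against.** The best defence is that the note speaks of outcome measures and gives pain scores as its example. The outcomes in 4.1 and 4.2 are a rating scale and a tablet count. An ED visit or admission is an outcome measure nowhere in the documents, so a careful reader would limit the note to recorded values unprompted. Pain is, moreover, not judged on one day alone: Secondary Aim 1 compares daily scores over two weeks, and Secondary Aim 2 compares opioid use. Objective 3 is specific to the catheter because only one arm has one. AEs count whether or not they are thought related to the intervention, and all of them go to the DSM.

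Much of this stands. It shows that the narrow reading is available and probably intended, and that pain itself is well covered by arm. It does not show that the narrow reading is required. Diary scores and opioid totals also do not record whether a participant returned to the ED.

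A reader might infer that the protocol excludes pain-related readmissions and prolonged stays from safety reporting. The documents do not support that. The note sits in the non-serious paragraph, criterion 3 has no exception for pain, clinically meaningful worsening of a pre-existing condition is an AE, and section 1.3 has inpatient encounters searched. For these events there is an ambiguity, not a stated exclusion.

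A reader might also infer that pain-related return visits are the main known harm of leaving out the catheter. That too goes beyond the text. The statement in 1.2 concerns TKA patients in general, and the same section reports a negligible pain difference in the pilot and equal same-day discharge with and without catheters.

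**Conclusion.** The concern holds in a limited form. Section 7.1 leaves it uncertain whether an ED visit for pain without admission is recorded as an AE. It leaves the handling of pain-related readmission or prolonged stay to an unstated reading of SAE criterion 3. Separately, and whichever reading is taken, the plan compares pain-related ED visits and admissions between arms nowhere, while catheter-related visits are counted. The primary noninferiority analysis is not affected. What suffers is the safety and cost comparison that the trial was set up to inform.

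The size is unknown, because the documents give neither a rate for these visits nor any indication of how staff would classify them. It is tempting to assume that 2% to 10% of participants have such an event, which gives 66 × 0.02 = 1.3 to 66 × 0.10 = 6.6 per arm, and to say that 1 to 7 per arm would go unreported. Those rates are not in the documents, and the result holds only if every event were excluded, which the text does not say. It is no estimate of the loss.

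The conclusion rests on two assumptions: that staff classify by the wording of 7.1, and that no separate document, such as the Data and Safety Monitoring Plan mentioned in 8.4, already settles the point.

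**What to change.** - Limit the note in 7.1 to recorded NRS scores and opioid quantities.
- State in 7.1 that an ED visit, readmission or prolonged stay for pain is recorded as an AE, and as an SAE where a criterion is met, in both arms.
- Tabulate pain-related ED visits and admissions by randomized arm in the DSM report and in the final safety table, next to the catheter-related visits.

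The ED and inpatient encounters are already to be extracted under section 1.3, so no new data source is needed. One date must be settled first, because the EMR extraction is placed at 30 days in 1.3, at 3 months in the synopsis and Appendix 1, and at 24 weeks in 6.8 and 6.9. The table needs a single window that starts at surgery.

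The change need not reach opioid side effects, which the note does not exclude, or unplanned clinic visits, which the EMR search does not target. The cost is a short edit to 7.1, one table row and a few more AE or SAE forms.

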7.2 REPORTING OF SERIOUS ADVERSE EVENTS

While the ACCESS study will not be conducted under an FDA IND or IDE, we will observe similar reporting requirements, modified for compatibility with the KPNC IRB guidelines. Deadlines for reporting are described below. The form for reporting will be the usual ACCESS SAE report form for early reportable SAE's and UP's and the relevant DSM report AE/SAE table (which will also be forwarded to the IRB following each DSM meeting)

Report to the IRB and DSM within 1 business day and at annual renewal

Unanticipated death at least possibly related to study (i.e., fatal UP)

Report to the IRB and DSM within 10 business days and at annual renewal

SAE's that are UP's

New safety information becomes available that is at the level of an UP

Report only at annual renewal (IRB) or at each DSM meeting

Death that is NOT a UP (i.e., all deaths that are not reported within 1 day)

7.3 REPORTING OF NON-SERIOUS ADVERSE EVENTS

All non-serious AE's will be recorded on the study AE form. All AE's will be reported in aggregate and individually to the IRB annually and to the DSM at each scheduled DSM conference call.

7.4 CRITERIA FOR TREATMENT DISCONTINUATION

Any ACC-allocated participant who exhibits a serious untoward reaction to the study ACC that, in the opinion of the investigators or the participant's treating physician, would render study continuation contrary to the best interest of the participant will be withdrawn from the study intervention. Any participant who is withdrawn from study intervention will be encouraged to continue all study-related data collection, in order to permit an intention-to-treat analysis with minimal data imputation.

7.5 CRITERIA FOR PARTICIPANT STUDY WITHDRAWAL

All participants will be encouraged to adhere to all study procedures even if they decline their randomized treatment assignment or prematurely remove the ACC, in order to permit an intention-to-treat analysis. If a participant expresses an intention to withdraw from the study prior to the two-week closeout time point, he/she will be questioned about the reasons for their intended withdrawal and attempts at resolving barriers to continued participation will be made (e.g., increasing contact with study investigators, shortening questionnaire time). Any participant may withdraw entirely from the study at any time.

8.0 STATISTICAL AND DATA CONSIDERATIONS

8.1 POWER CALCULATIONS

As a noninferiority study, this trial has been powered to ensure that the lower limit of the 95% confidence interval does not cross the pre-specified noninferiority margin if the null hypothesis is rejected. We have made several conservative assumptions to ensure that the lack of a finding of noninferiority is not due to a lack of statistical power: we assumed a statistical power of 95% (very high power to increase the likelihood that the lower bound of the one-sided 95% CI will be on the null side of the noninferiority margin if usual care without an ACC is truly noninferior to use of an ACC), we have used a one-sided 95% CI of 0.025, and the variance estimate was obtained from a sample of patients similar to those intended for recruitment from the SLN Medical Center.

Special care was taken in establishing the noninferiority margin. Note that the goal of this study is not to demonstrate noninferiority in an absolute clinical sense, but to provide sufficient information to the orthopedic community in order to inform the decision regarding placement of ACC's. This insight led the PI ([name]) to conduct an e-mail poll of his colleagues, asking for their perception of the MCID that would lead to a change in practice with respect to placing ACC's. [name] received 19 replies with the following response distribution:

0.5 points: 1 (5.3%)
1.5 points: 2 (10.5%)
2.0 points: 11 (57.9%)
3.0 points: 4 (21.1%)
4.0 points: 1 (5.3%)

Mean: 2.18 points / Median: 2.0 points

Given the median MCID of 2 points, we originally chose a conservative value of 1.5 points (0.5 points below the median) for this trial, in order to maximize credibility of the results. This value was revised upward to 2.0 (see below) in version 1.1 of the protocol.

The following describes the methods and assumptions used for calculation of the necessary sample size for this study (power calculations were performed with the PASS power-analysis package (33)):

H_0 : The mean NRS pain score in the active-treatment group is less than the mean NRS pain score in the control group on the second postoperative day

H_A : The mean NRS pain score in the active-treatment group is not less than the mean NRS pain score in the control group on the second postoperative day

α : 0.025 (1-tailed) [standard practice for noninferiority trials (34)]

β : 0.02 (Power=98%)

Standard deviation = 2.64 (from an interim analysis of the blinded data of 98 enrolled participants)

Noninferiority margin (δ) = 2.0 points

Randomization ratio: 1:1

Test on which calculations based: z-test

Number of evaluable randomized participants required = 60 per group; Total number required = 120

Total number of recruited participants required accounting for 10% withdrawals = 132 (66 per group)

This sample size will require recruitment of 132 participants/64.5 weeks = 2.1 participants per week (the SLN Medical Center orthopedics group performs approximately 20 TKAs per week).

Note on interim data examination to resize the trial: The sample size calculations described above relied on an estimate of the standard deviation of the primary outcome, which was calculated using a sample of 163 KPNC SLN members who underwent TKA in 2018. Although we expect that the standard deviation of the primary trial outcome will align with the estimates used in the sample size calculation, deviations in the estimate used may have a substantial impact on sample size and power. Because of this, we plan to estimate the standard deviation of the primary outcome using interim data mid-way through the trial (the first 59 patients pooled from both trial arms) (35), and will re-calculate the sample size to ensure that our original calculations are reasonably appropriate to the observed

variance. Note that there is no inter-group comparison and, therefore, no cost to the experimentwise alpha.

Note on the revised calculations: Blinded study data were examined twice, most recently after 98 participants were enrolled and the assumed standard deviation of 2.04 was revised upward to 2.64 based on this analysis. In addition, the survey of knee-arthroplasty specialty KPNC orthopedic surgeons conducted by the Principal Investigator showed that 84% of the 19 respondents would set the noninferiority margin at 2.0 points or more. In the original power calculations, we assumed a noninferiority margin of 1.5 points, in order to be highly conservative. However, after further reflection and sensitivity analyses, we found that adopting such a strict noninferiority margin could substantially impair our ability to declare noninferiority for an observed nonzero difference. Therefore, we reset the noninferiority margin back to 2.0 points, consistent with the responses to the orthopedist survey. Finally, in order to retain a very high likelihood of affirming noninferiority if the point estimate of the between-group difference in the outcome pain scores was less than the noninferiority margin, we decreased the beta to 0.02 (power = 0.98).

